## **6 Study Drug**

### **6.1 Description**

Noxafil delayed-release tablets are available as yellow, coated, oblong tablets, debossed with "100" on one side containing 100 mg of posaconazole.

### **6.2 Treatment Regimen**

Posaconazole (Noxafil®) delayed-release tablets: Loading dose: 300mg (three 100mg delayed-release over-encapsulated tablets) twice a day on the first day, then Maintenance dose: 300mg (three 100mg delayed-release over-encapsulated tablets) once a day, starting on the second day. Duration of therapy will be 12 weeks.

### **6.3 Preparation and Administration of Study Drug**

To maintain study blind, placebo capsules will be manufactured using blue gelatin capsules, size 00, and filled with Cellulose Microcrystalline. Posaconazole tablets will be over-encapsulated, using the same blue gelatin capsules, size 00, and back-filled with Cellulose Microcrystalline.

Posaconazole will be self-administered by the subjects, with the first dose observed at the time of the baseline visit. Subjects will be advised to swallow the capsules whole, and to not divide, crush or chew. The capsules should be taken with food to enhance the oral absorption of posaconazole and optimize plasma concentrations.

### **6.4 Subject Compliance Monitoring**

Subjects need to keep the capsule containers and bring them to follow up visit. Compliance will be evaluated by the counts of unused tablets. If a deviation from protocol is identified, the investigators will inquire as to the reason for study deviation during the corresponding patient encounter. Non-compliance related to study medication regimen and (i.e., less than 80% or more than 120% of recommended dosing) and not due to adverse events will be evaluated by the Investigator who will encourage subject to follow the medication regimen prescribed. Patients who remain significantly non-compliant with the drug regimen and not due to adverse events for two consecutive visits will be withdrawn from study or earlier at the discretion of the PI. The subject will then complete the final follow-up visit per protocol.

### **6.5 Prior and Concomitant Therapy**

The following concomitant therapies are allowed as long as a stable dose was administered per eligibility criteria:

- Biologic agents (infliximab, adalimumab, certolizumab, ustekinumab, vedolizumab)
- Immunomodulators (azathioprine/6-mercaptopurine)
- Oral 5-aminosalicylates or sulfasalazine

Oral corticosteroid preparations (maximum budesonide 9 mg/day, or prednisone 20 mg/day or equivalent) will be allowed as long as the dose has been stable dose for two weeks prior to screening. The dosage may not be reduced during the 12-week study period without premature discontinuation from the trial. Any dosage increases beyond that prescribed at the start of the trial will result in early withdrawal from study due to progression of Crohn's disease.

Concomitant prescribed therapies, non-prescription supplements, and herbal preparations which affect hepatic metabolism, antibiotics, probiotics, and antidiarrheals will not be allowed during the study. Drugs predominantly metabolized by CYP3A4 may be increased by posaconazole. Examples of drugs prohibited during the current proposed trial include, but are not limited to: cyclosporine, tacrolimus, sirolimus, simvastatin and other HMG-CoA inhibitors, midazolam, rifabutin, phenytoin, ritonavir, atazanavir, and upadacitinib.

Data regarding the composition, dosage, dosing schedule, route of administration, and initiation/end dates of therapy will be recorded for each concomitant therapy.

### **6.6 Packaging**

Noxafil delayed-release tablets are available as yellow, coated, oblong, debossed with "100" on one side containing 100 mg of posaconazole. Bottles with child-resistant closures of 60 delayed-

release tablets (NDC 0085-4324-02). Upon arrival at site, tablets will be over-encapsulated with blue gelatin capsules.

### **6.7 Receiving, Storage, Dispensing and Return**

Store at 20-25°C (68-77°F), excursions permitted to 15-30°C (59-86°F) [see USP Controlled Room Temperature].

#### **6.7.1 Receipt of Drug Supplies**

Upon receipt of the of the study treatment supplies, an inventory will be performed, and a drug receipt log filled out and signed by the person accepting the shipment. Designated study staff will verify that the shipment contains all the items noted in the shipment inventory. Any damaged or unusable study drug in a given shipment will be documented in the study files.

#### **6.7.2 Storage**

Store at 20-25°C (68-77°F), excursions permitted to 15-30°C (59-86°F)

#### **6.7.3 Dispensing of Study Drug**

Patients will be dispensed a 2-week supply of study drug (or placebo) at each of the following study visits: baseline (week 0), and weeks 2, 4, 6, 8, and 10. Study drug reconciliation will be performed to document drug assigned, drug consumed, and drug remaining. This reconciliation will be logged on the drug reconciliation form and signed and dated by the study team.

Patients who are eligible to receive open label posaconazole will be dispensed a 4-week supply of study drug at weeks 12, 16, and 20.

#### **6.7.4 Return or Destruction of Study Drug**

At the completion of the study, there will be a final reconciliation of drug shipped, drug consumed, and drug remaining. This reconciliation will be logged on the drug reconciliation form, signed and dated. Any discrepancies noted will be investigated, resolved, and documented prior to return or destruction of unused study drug. Drug will be destroyed per research pharmacy discretion.

### **6.8 Placebo**

Placebo capsules will be developed for this study and will duplicate the size, color and shape of the over-encapsulated Noxifil®.

## **7 Study Procedures**

### **7.1 Screening (Week -4 to Week 0)**

After informed consent is given, eligibility will be evaluated over a period of four weeks. The study investigators will discuss with the patient the purpose, obligations, and risks of the study.

The following tasks will be conducted or scheduled at the initial Week -4 visit:

- Complete medical history: date of diagnosis; extent of disease; date and reason for CD-related hospitalizations; past medical history (including prior invasive fungal infection, arrhythmia, chronic kidney disease stage III or greater, uncontrolled diabetes mellitus, cirrhosis, and major psychiatric disorder); alcohol and drug history; and extra-intestinal manifestations.

CONFIDENTIAL

This material is the property of Cedars-Sinai Medical Center.

- Medication history: list of current medications including date of initiation, length of current dosing regimen, current dose, current frequency, current route of administration; list of prior medications, including clinical response to medication and reason for medication withdrawal; all non-prescription medications, non-prescription supplements, and herbal preparations used within last twelve weeks.
- Complete physical examination, height, vital signs, and weight.
- Laboratory studies: serum  $\beta$ -hCG in women of childbearing potential, safety laboratory tests (serum chemistries, complete blood count with automatic differential, lipid panel, hemoglobin A1c, urinalysis), and stool studies (stool ova and parasitology, culture, and C. difficile toxin assay,
- 12-lead EKG.
- Chest radiography posteroanterior and lateral (if patient meets all of the above eligibility requirements) if not performed within last 12 months.
- Bowel movement diary instructions.
- Eligibility assessment based on collected data.
- Colonoscopy to be scheduled within one week of baseline visit, with SES-CD score
  - Mucosal biopsies will be collected from the Ileum, Right colon, and Left Colon. 2 biopsies from most inflamed area of each region will be taken. One tissue will be placed in a solution of RNALater, and the other tissue will be placed in Formalin.
  - and Washings for fungome analyses
- Stool collection for microbiome analysis, stored at -70C, and batch shipped every 6-Months.
- Blood for transcriptomics.
- Blood for genetics (if CARD9 status is not known)

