| Diagnosis and Inclusion Criteria | 
Subjects (n=24) will be individuals with active Crohn's disease (SES-CD <math>\geq</math> 6 AND Crohn's disease activity index score >220) despite use of conventional therapy. In this 40-week trial, subjects will be administered posaconazole (Noxifil®, Merck) 300mg twice daily for 1 day followed by 300mg daily for 12 weeks, or matching placebo. At 12 weeks, subjects will undergo assessment for response, and treatment assignments will be unblinded. Based on active disease criteria at the end of induction and treatment assignment, subjects will either be observed off posaconazole over the next 24 weeks, or (if they are deemed to be a 'non-responder' AND were assigned to placebo) will have the option to enroll into a twelve-week open label period, followed by a twelve week follow up period. In addition to the treatment intervention, subjects also will provide samples for parallel translational studies including blood for genetic analysis, stool samples for biomarker and microbial composition analysis, and biopsies for mucosal gene expression analysis.
 
Inclusion Criteria
 
 
1. Male or female patients <math>\geq</math> 18 years of age.
 
2. A diagnosis of CD with minimum disease duration of 6 months with involvement of the ileum and/or colon documented on colonoscopy
 
3. Have an endoscopically-confirmed active Crohn's disease with active disease defined by SES-CD <math>\geq</math> 6 (<math>\geq</math>4 if ileal only), AND active symptoms of Crohn's disease (CDAI score >220) at Baseline Visit.
 
 |

|  |   |
|--|---|

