| Mucosal Washing                           | X |   |   |   |   |   |   | X               |                 |                 |                 |                 |                 | X |
| Mucosal biopsies for RNA Later & Formalin | X |   |   |   |   |   |   | X               |                 |                 |                 |                 |                 | X |
| Study therapy management                  |   |   |   |   |   |   |   |                 |                 |                 |                 |                 |                 |   |
| Study therapy dispensed                   |   | X | X | X | X | X | X | X  | X  | X  |                 |                 |                 |   |
| Study therapy accountability              |   |   | X | X | X | X | X | X               | X               | X               | X               |                 |                 |   |
| Adverse events assessment                 |   | X | X | X | X | X | X | X               | X               | X               | X               | X               | X               | X |
| Crohn's disease assessments               |   |   |   |   |   |   |   |                 |                 |                 |                 |                 |                 |   |
| Bowel movement diary                      | X | X | X | X | X | X | X | X               | X               | X               | X               | X               | X               | X |
| Crohn's Disease Activity Index            |   | X | X | X | X | X | X | X               | X               | X               | X               | X               | X               | X |
| PRO2                                      |   | X | X | X | X | X | X | X               | X               | X               | X               | X               | X               | X |
| SES-CD score                              | X |   |   |   |   |   |   | X               |                 |                 |                 |                 |                 | X |
| Quality-of-Life assessments               |   |   |   |   |   |   |   |                 |                 |                 |                 |                 |                 |   |
| IBDQ                                      |   | X | X | X | X | X | X | X               | X               | X               | X               | X               | X               | X |

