| SF-36                                     |   | X | X | X | X | X | X | X               | X               | X               | X               | X               | X               |   |

Subjects who discontinue early will undergo all tests and procedures according to the Week 12 visit at the time of discontinuation or as soon as possible thereafter

Medical history include date of symptom onset, date of diagnosis, and medication/surgical history. Medical history is detailed in Section 6.

The first eligibility assessment will be performed after all other required study assessments for the screening visit except colonoscopy. The second eligibility assessment will be performed after review of concomitant medications, urine pregnancy test, and colonoscopy.

Targeted physical examination focuses on symptoms, as well as on eyes, throat, lymph nodes, cardiopulmonary systems, abdomen, musculoskeletal, extremities, and skin.

Only for females with childbearing potential excluding those with bilateral tubal ligation or at least one-year post-menopause.

Safety laboratory tests include serum chemistries, complete blood count with automatic differential, electrolyte panel (potassium, magnesium, calcium, sodium, chloride, phosphate), lipid panel

Stool studies include stool ova and parasitology, culture, and *C. difficile* toxin assay Drawn only if not performed in the last 4 weeks

These tests will be read by non-study physicians. Chest Xray posterior/anterior and lateral if not performed in the last 12 months

Baseline colonoscopy will be performed between Week -4, Day 1 and Week 0, Day 1, after eligibility assessment. Bowel prep will be dispensed or prescribed at Week -4.

Dispensing for patients participating in Open-label

Only required for participants receiving Open-label drug

 gene testing will only be performed on patients whose CARD9 status is unknown.

CONFIDENTIAL

This material is the property of Cedars-Sinai Medical Center.

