## 5.2 Inclusion Criteria

1. Male or female patients  $\geq 18$  years of age.
2. A diagnosis of CD with minimum disease duration of 6 months with involvement of the ileum and/or colon documented on colonoscopy
3. Have an endoscopically-confirmed active Crohn's disease with active disease defined by SES-CD  $\geq 6$  ( $\geq 4$  if ileal only), AND active symptoms of Crohn's disease (CDAI  $>220$ )
4. Subjects receiving oral aminosalicylates (at a stable dose for 2 weeks prior to baseline), immunomodulators (at a stable dose for 4 weeks prior to baseline), anti-TNF, anti IL12/23, or anti-integrin therapy (at stable maintenance doses for  $\geq 8$  weeks) may continue their use during the study.
5. Subjects receiving oral corticosteroids may continue their use during the study provided the dose (prednisone up to 20 mg/day, budesonide up to 9 mg/day) has been stable for two weeks prior to screening.
6. Lab findings of hypokalemia, hypomagnesemia, or hypocalcemia are eligible, provided electrolyte abnormalities are corrected and stable prior to study enrollment.
7. Have had age-appropriate and disease-duration-appropriate colon cancer screening without unresected dysplasia.
8. Women of childbearing age, excluding those with prior bilateral tubal ligation or at least one-year post-menopause, must not be pregnant, lactating, or planning to become pregnant. They must agree to use effective contraception throughout the study period.
  - a. Option 1: Any one of the following highly effective methods: hormonal contraception for example, birth control pills, injection, implant, transdermal patch, vaginal ring); intrauterine device (IUD); tubal ligation (tying your tubes); or a partner with a vasectomy
  - b. Option 2: Any two of the following effective methods: male or female condom PLUS one of the following additional barrier methods (a)diaphragm with spermicide; (b) cervical cap with spermicide; or (c) contraceptive sponge with spermicide
9. Subjects must be able to provide informed consent and understand, agree with, and be able to adhere to daily diary entries, all scheduled visits, tests, procedures, and protocol in English.

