#### **5.4 Subject Recruitment and Screening**

Potential study candidates will be identified from the Cedars-Sinai Inflammatory Bowel Disease Center genetic database (MIRIAD) and Mayo Clinic's IBD Biobank; all MIRIAD and Biobank participants have previously provided written, informed consent to participate in genetic research and to be contacted for potential research opportunities. Patients who have CARD9 risk allele will be notified of an opportunity to participate in this trial at the time of a routine clinical encounter, if deemed appropriate by their treating provider. They will be provided with information about the study, and if the study candidate is interested in study participation, they will be scheduled for the screening visit.

Patients who wish to participate in this research, who have not previously had their CARD9 risk allele testing performed or who are not in MIRIAD or Mayo Clinic's IBD Biobank, will have an opportunity to provide a blood sample for genetic testing of CARD9, once Informed Consent to participate has been provided.

At the screening visit, patients will be asked to provide informed consent for the study. A complete medical history will be taken including list of current and recent medications. A complete physical examination, including height, weight, vital signs will be performed. Safety laboratory studies, pregnancy test, stool studies, and EKG will be performed at this visit (stool may be provided after the visit). Chest radiography will be performed. Then, patients meeting eligibility will be scheduled for baseline colonoscopy. Patients meeting eligibility criteria will be scheduled for the baseline visit.

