## **7.2 Baseline visit (week 0)**

The following tasks will be conducted at this visit:

- Assessment of concomitant medications.
- Complete physical examination, vital signs, and weight.
- Laboratory studies: urine pregnancy test in women of childbearing potential, hsCRP, serum chemistries, complete blood count with automatic differential, lipid panel, and stool calprotectin.
- Calculation of CDAI and PRO2 scores
- Eligibility assessment based on collected data.
- Study therapy dispensed and instructions on use given.
- Adverse event monitoring.
- Review of bowel movement diary.
- IBDQ and SF-36 assessments.
- Randomization of subjects to treatment arm via REDCap by research pharmacist. (Both subject and clinical staff will be masked to treatment group assigned.)

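### No CDAI or PRO2 is calculated before the screening colonoscopy, so candidates can have the procedure and six research biopsies before failing CDAI >220 at baseline

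*Combined protocol and SAP*

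**What the plan says.** Inclusion criterion 3 has an endoscopic part (SES-CD) and a symptom part. The Protocol Synopsis ties the symptom part to a visit: "AND active symptoms of Crohn's disease (CDAI score >220) at Baseline Visit". Section 5.2 gives the same threshold without naming a visit.

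Section 7.1 lists the first colonoscopy among the screening tasks: "Colonoscopy to be scheduled within one week of baseline visit, with SES-CD score". Biopsies from three regions and washings are taken at that procedure. The 7.1 list contains neither CDAI nor PRO2. Section 7.2 is the first to include "Calculation of CDAI and PRO2 scores". Table 1 agrees: the Screening cells for CDAI and PRO2 are blank, while colonoscopy, mucosal washing, biopsies and SES-CD are all marked there.

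Table 1, footnote 3, sets out two eligibility assessments. "The first eligibility assessment will be performed after all other required study assessments for the screening visit except colonoscopy"; the second follows colonoscopy. Section 5.4 gives the same order. After the screening tests, it says: "Then, patients meeting eligibility will be scheduled for baseline colonoscopy". The baseline visit comes next.

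**The concern.** The plan means to screen out ineligible patients before colonoscopy. The pre-colonoscopy assessment can do so on laboratory results, EKG, stool pathogens and medications. It has no calculated value for the symptom half of criterion 3, so a candidate below the threshold is not identified until after the most burdensome screening procedure.

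What is at stake is burden on patients: bowel preparation, colonoscopy and research biopsies in people who then do not meet the entry criteria. The primary endpoint, power, blinding and treatment comparison are not affected.

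**Working it through.** The plan states no figure on this point, so there is none to reproduce. The check is on the order of steps, followed by an illustration of scale.

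**Order of steps**

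| Step | Source | CDAI or PRO2 available? |
|---|---|---|
| Screening tests, diary instructions | 7.1, Table 1 | Not calculated |
| First eligibility assessment | Table 1 footnote 3, 5.4 | No |
| Colonoscopy, biopsies, washings, SES-CD | 7.1, Table 1 | No |
| Baseline visit: CDAI and PRO2, then second eligibility assessment | 7.2, Table 1 | Yes, for the first time |

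Footnote 10 also places the procedure after an eligibility assessment ("Baseline colonoscopy will be performed between Week -4, Day 1 and Week 0, Day 1, after eligibility assessment"). The only assessment before colonoscopy is the first one, which lacks the score.

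**Burden per candidate.** Section 7.1 specifies 2 biopsies in each of 3 regions: 2 × 3 = 6, plus washings. The provision for future research in Section 11.4 covers blood and stool, not biopsy tissue.

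**Scale (assumed rates).** Let x be the share of endoscoped candidates who then fail CDAI >220, treated as the only reason for failing after colonoscopy. To enrol 24, the number endoscoped is 24/(1 − x), and the number failing CDAI is 24/(1 − x) − 24.

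- x = 0.10: 24/0.90 = 26.7, so 2.7 failures (about 3)
- x = 0.25: 24/0.75 = 32.0, so 8.0 failures
- x = 0.40: 24/0.60 = 40.0, so 16.0 failures

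Under this simplification, the counts are a ceiling on what an early check could save. A patient above 220 at screening who falls to 220 or below by week 0 would still be endoscoped.

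**Does an earlier score fit the schedule?** The CDAI in Appendix 1 needs 7 diary days. The full screening window is 4 × 7 = 28 days. If colonoscopy falls in the last 7, 28 − 7 = 21 days come before it. That is enough for one 7-day diary, with 21 − 7 = 14 days for repeats. A shorter screening period, or a colonoscopy at the early end of footnote 10's window, would leave less.

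**Are the inputs there?** Mostly. Weight, physical examination and a complete blood count (which includes haematocrit, Section 8.2) are collected at screening, and the diary starts then. But Appendix 1 needs 7 daily ratings of general well-being, and the diary described in Section 8.1.1 does not list them. Only diary instructions are given at the Week -4 visit, so no 7-day record exists on that day.

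**The case against.** The strongest reply is that this is a deliberate and consistent choice. The synopsis fixes CDAI at the baseline visit, and Table 1 and Section 7.2 follow it. Candidates are also not endoscoped with no symptom information: the diary runs from screening, stool frequency and pain are diary items, and Section 5.4 requires the treating provider to think the trial appropriate. All of this stands. It means that the baseline CDAI should stay as the deciding value, and that what is missing is a calculated score before colonoscopy, not all knowledge of symptoms.

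A second reply also stands in part. A single hard cut-off at screening would shut out a patient at or below 220 then but above 220 at baseline, who qualifies under the synopsis. In a 24-subject trial restricted by genotype that matters, so the check has to be provisional and repeatable.

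A reader might infer more than the documents support:

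- **The procedure is done for nothing.** The documents do not say whether the colonoscopy has clinical value to the patient. They only name no trial use for the tissue.
- **Patients who fail can never be randomised.** Rescreening is not addressed either way.
- **Central reading and laboratory processing are wasted.** The synopsis specifies central reading for the Week 12 endpoint. Neither statement of criterion 3 says that the eligibility SES-CD is centrally read, and nothing says that biopsies are analysed before randomisation.
- **All CDAI inputs already exist at screening.** The well-being rating is missing from the diary description, and a 7-day record takes a week to build.

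**Conclusion.** The point holds as a modest, inexpensive improvement to screening. No CDAI or PRO2 is calculated before colonoscopy, so a candidate can have the procedure, washings and 6 research biopsies before failing CDAI >220. Section 7, Table 1 with its footnotes and Section 5.4 all agree on this order.

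The size is unknown, because the documents give no CDAI failure rate. Assumed rates of 10%, 25% and 40% give at most about 3, 8 and 16 such colonoscopies in enrolling 24. It would be wrong to read all of these as avoidable: CDAI can change before week 0, so an early check would prevent only part of them. Patients who fail on SES-CD alone need the colonoscopy in any case.

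**What to change.** 1. In Section 7.1, Table 1 and footnote 3, add a provisional CDAI/PRO2 calculation from 7 completed diary days before bowel preparation, using screening haematocrit, weight and examination. Schedule the research colonoscopy once the symptom criterion is met on those data.
2. Allow the calculation to be repeated on later diary days within the four-week window, so that patients who would qualify at baseline are not excluded. Keep the baseline CDAI as the deciding value.
3. Add general well-being to the diary description in Section 8.1.1. The baseline CDAI needs it anyway.
4. Reconcile the opening paragraph of Section 5, which defines active symptoms by PRO2, with the CDAI criterion in the synopsis and Section 5.2, so that the early check and the final assessment use one definition.

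The cost is protocol wording and a diary change, at least one week of diary, and a diary return or contact before colonoscopy. Screening will be slightly slower.
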